8.2.3 Rescue Therapy

In case **HbA1c is above 8% at Week 12 or later on**, the Investigator will receive an alert issued by the central laboratory and should ensure that no reasonable explanation exists for insufficient glucose control and in particular that there is no intercurrent disease which may jeopardize glycemic control (eg, infectious disease), that the treatments are given at the planned dose and compliance to treatment and diet and lifestyle is appropriate. HbA1c assessment should be scheduled at next visit (if next visit is a phone call, it should be replaced by an unscheduled visit at site) or within 4 weeks. If appropriate corrective action fails and if the repeated HbA1c remain above 8%, a rescue therapy should be considered according to the Investigator's judgment.

In the FRC arm:

- rescue therapy is recommended only if further dose titration is not possible, ie, the patient is already at the maximum daily dose of 60 units;
- rapid acting insulin (insulin- glulisine when available) is suggested and should be started as a single daily administration to be given at the main meal of the day (excluding breakfast);
- basal insulin is not allowed in the FRC arm.

In the GLP-1 RA arm:

- suggested rescue therapy is basal insulin at the investigator's discretion.

During the extension period, suggested rescue therapy is rapid acting insulin (insulin- glulisine when available) for all patients.

All assessments planned at the end of the randomized treatment visit (V28) are to be performed before initiating rescue therapy during the randomized treatment period. All assessments planned at the end of extension period treatment visit (V35) are to be performed before initiating rescue therapy during the extension period. After these assessments are completed and rescue therapy initiated, the patient will remain in the study and continue to administer the study treatment (including background therapy). The planned visits and assessments should be performed until the last scheduled visit. Patients receiving rescue therapy during the randomized treatment period and eligible for the extension period can continue it as required.

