2.1.4 Safety endpoints

The safety endpoints are assessed by:

- Symptomatic hypoglycemia (documented, probable, severe symptomatic hypoglycemia),
- Adverse events (AEs), serious adverse events (SAEs), and AE of special interest (AESI),
- Safety laboratory values,
- Vital signs,
- Electrocardiogram (ECG).
- Immunogenicity (antibody variables, FRC group): anti-insulin and anti-lixisenatide antibodies.

Observation period

The observation period of safety data will be divided into 3 segments:

- The pre-treatment period is defined as the time between the date of the informed consent and the first injection of open-label IMP,
- The on-treatment period of the whole study for daily formulation is defined as the time from the first injection of open-label IMP up to 3 days (1 day for symptomatic hypoglycemia) after the last injection of IMP, regardless of the introduction of rescue

therapy. The on-treatment period of the whole study for weekly formulation is defined as the time from the first injection of open-label IMP up to 9 days (7 day for symptomatic hypoglycemia) after the last injection of IMP, regardless of the introduction of rescue therapy.

- The 26-week on-treatment period is defined as follows:
 - For patients who are not eligible to enter the extension period, the 26-week on-treatment period is defined as
 - For patients receiving daily IMP: time from the first injection of open-label daily IMP up to 3 days (1 day for symptomatic hypoglycemia) after the last injection of daily IMP, regardless of the introduction of rescue therapy.
 - For patients receiving weekly IMP: time from the first injection of open-label weekly IMP up to 9 days (7 day for symptomatic hypoglycemia) after the last injection of weekly IMP, regardless of the introduction of rescue therapy.
 - For the patients who are eligible to enter the extension period, the 26-week on-treatment period is defined as the time from the first injection of open-label IMP up to V28/Week 26 visit (or Day 183 if V28/Week 26 visit is missing).
- The post-treatment period is defined as the time starting 4 days (2 days for symptomatic hypoglycemia) after the last injection of open-label daily IMP, or starting 10 days (8 days for symptomatic hypoglycemia) after the last injection of open-label weekly IMP (after the on-treatment period of the whole study).

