2.4.3.1 Extent of investigational medicinal product exposure

The extent of open-label IMP exposure will be assessed by the duration of IMP exposure during the study.

The duration of treatment exposure will be the total number of days of administration of the open-label IMP, regardless of unplanned intermittent discontinuations.

The duration of daily IMP exposure will be calculated as:

(Date of the last open-label IMP injection – Date of the first open-label IMP injection) + 1.

The duration of weekly IMP exposure will be calculated as:

(Date of the last open-label IMP injection – Date of the first open-label IMP injection) + 7.

Duration of IMP exposure (days) will be summarized using continuous descriptive statistics (N, mean, SD, minimum, median, and maximum). The cumulative exposure in patient years, defined as the sum of patients' duration of IMP exposure, will also be provided. In addition, duration of IMP exposure will be summarized categorically by counts and percentages for each of the following categories, and cumulatively according to these categories:

- 1 to 14 days,
 - 15 to 28 days,
 - 29 to 56 days,
 - 57 to 84 days,
 - 85 to 126 days,
 - 127 to 168 days,
 - 169 to 182 days,
 - 183 to 210 days,
 - 211 to 238 days,
 - 239 to 294 days,
 - 295 to 364 days
 - > 364 days.
- The exposure parameters are provided for the 26-week randomized treatment period and for the whole study treatment period (FRC group only), respectively.

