2.4.5.1 Analyses of symptomatic hypoglycemia

Analyses of symptomatic hypoglycemia will be performed on the on-treatment period, as defined in [Section 2.1.4](#). Unless specified otherwise, all analyses described below will be performed by treatment group for the 26-week on-treatment period and for FRC group for the on-treatment period of the whole study including the extension period, respectively.

The number (%) of patients with any symptomatic hypoglycemia recorded in the dedicated eCRF “Symptomatic hypoglycemia” page and meeting protocol definitions for severe, documented or probable symptomatic hypoglycemia described in [Section 2.1.4.1](#) and with at least 1 symptomatic hypoglycemia by category (ie, severe, documented, and probable symptomatic hypoglycemia) will be summarized by treatment group for the on-treatment period, as well as the incidence rate in patient years. Two types of incidence rates will be presented: the number of patients with at least 1 event per patient years (calculated as the number of patients with at least 1 event / total exposure in patient years), and the number of events per patient years (calculated as the number of events / total exposure in patient years). Note: here exposure is duration of on-treatment, ie, duration of IMP treatment in days +1 for daily formulation and duration of IMP treatment in days + 7 for weekly formulation (see [Section 2.1.4](#)).

The above summary will also be provided for the on-treatment period before introduction of rescue therapy. In addition, all the above summary will be provided for documented symptomatic hypoglycemia with plasma glucose <60 mg/dL [3.3 mmol/L].

- The summary of frequency and incidence rate in patient years for documented symptomatic hypoglycemia will be provided as appropriate by gender (Male, Female), age group (<50, ≥50 to <65, ≥65 to < 75, ≥75 years of age), race (American Indian or Alaska Native, Asian/Oriental, Black, Native Hawaiian or Other Pacific Islander, White, Other), GLP-1 receptor agonist subtype (QD/BID formulations, QW formulations) at screening, SGLT2 inhibitor use (Yes, No) at screening (if each category contains sufficient number of patients), and insulin and lixisenatide dose groups (FRC group only).
- The summary of frequency and incidence rate in patient years for documented symptomatic hypoglycemia will be provided by anti-lixisenatide and anti-insulin glargine

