2.5.3 Missing data

For categorical variables, patients with missing data are not included in calculations of percentages unless otherwise specified. When relevant, the number of patients with missing data is presented.

Derived variables will be considered missing if any of the original variables required to calculate them are missing. For example, if either a baseline assessment or an endpoint assessment is missing for a particular patient, then change from baseline at endpoint will be missing. Depending upon the assessment, analyses may not include all patients in the analysis population, because certain patients in the intended population may have missing data.

Incomplete date of first injection

Date of first injection is the first non-missing start date of open-label IMP completed in the eCRF “Investigational medicinal product administration” module.

For patients who are randomized and dispensed a treatment kit but who are lost to follow-up just after Visit 3 (only the treatment kit number is reported in the eCRF “Investigational medicinal product administration” module without any dose information), the date of first injection will be

imputed using the Visit 3 date. When a patient is randomized but not dispensed a treatment kit, the “Investigational medicinal product administration” module should be blank. In this case, the patient will be considered as randomized but not treated, unless the patient’s disposition is not confirmed.

Handling of computation of treatment duration if IMP end of treatment date is missing

For the calculation of the 26-week randomized treatment duration, the date of the last injection of randomized open-label IMP is equal to the date of last administration reported on the eCRF “Treatment Status” page. If this date is missing, the randomized exposure duration should be kept as missing. For the calculation of the treatment duration of whole study for patients participating the extension period, the date of the last injection of IMP is equal to the date of last administration reported on the eCRF “Treatment Status for Extension Phase” page. If this date is missing, the exposure duration should be kept as missing.

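### Does the +7 days in the SAP's hypoglycaemia exposure note give weekly-drug control patients too much person-time?

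*SAP*

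**What the plan says.** SAP 2.4.5.1 places the symptomatic hypoglycaemia analyses on the on-treatment period of SAP 2.1.4. It plans two rates per patient-year: patients with at least one event, and events. A note says that exposure here means the on-treatment duration, explains this as "duration of IMP treatment in days +1 for daily formulation and duration of IMP treatment in days + 7 for weekly formulation", and refers to Section 2.1.4.

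SAP 2.1.4 sets the window. For weekly drugs it runs "up to 9 days (7 day for symptomatic hypoglycemia) after the last injection of weekly IMP", and the post-treatment period begins "starting 10 days (8 days for symptomatic hypoglycemia) after the last injection of open-label weekly IMP". For daily drugs the hypoglycaemia tail is 1 day. For patients eligible for the extension, the 26-week window is the "time from the first injection of open-label IMP up to V28/Week 26 visit (or Day 183 if V28/Week 26 visit is missing").

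SAP 2.4.3.1, on extent of exposure, has its own formulas: last minus first injection + 1 for daily drugs, and for weekly drugs a formula ending in "Date of the first open-label IMP injection) + 7".

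SAP 2.4.5.1 continues: "The above summary will also be provided for the on-treatment period before introduction of rescue therapy".

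**The concern.** The note adds its tail to a quantity that the SAP never defines under that name. An analyst looking for it would find only the 2.4.3.1 formulas. SAP 2.5.3 encourages that step: its paragraph on computing treatment duration says "If this date is missing, the randomized exposure duration should be kept as missing", so treatment duration and exposure duration look like the same thing.

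The 2.4.3.1 weekly formula already contains a 7-day allowance, so adding 7 more counts the dosing interval twice. The surplus days fall in the post-treatment period, where person-time would accrue but no event could be counted. FRC is a daily drug, so only control patients on Bydureon, Tanzeum or Trulicity would be affected. Their rate would be too low and the FRC-to-control contrast a little too wide. The planned summary by GLP-1 receptor agonist subtype would show the full effect in the once-weekly control group.

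A second worry concerns the pre-rescue summary. Under Protocol 8.2.3, after rescue starts "the patient will remain in the study and continue to administer the study treatment (including background therapy"), so a formula tied to the last injection would run past the start of rescue.

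**Working it through.** **Inputs.** Let L be last minus first injection date, in days. SAP 2.5.4 makes the first injection Day 1, so days are counted inclusively. The windows come from SAP 2.1.4, the candidate base durations from SAP 2.4.3.1, and the tails (+1, +7) from SAP 2.4.5.1.

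**Target, from 2.1.4.**
- Daily: first injection to 1 day after the last = L + 2 days.
- Weekly: first injection to 7 days after the last = L + 8 days.

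**Reading A: base taken from 2.4.3.1.**
- Daily: (L + 1) + 1 = L + 2. Matches.
- Weekly: (L + 7) + 7 = L + 14. Exceeds the window by (L + 14) − (L + 8) = 6 days, namely days 8 to 13 after the last injection.

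**Reading B: base is first to last injection, inclusive, for every formulation (L + 1).**
- Daily: (L + 1) + 1 = L + 2. Matches.
- Weekly: (L + 1) + 7 = L + 8. Matches.

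Only Reading B satisfies the note's own statement that exposure is the on-treatment duration.

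**Size under Reading A, per weekly completer.** The documents do not fix the number of injections, so 25 to 27 is assumed.

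| Injections | L | Reading A (days) | Window (days) | Rate too low by |
|---|---|---|---|---|
| 25 | 168 | 182 | 176 | 1 − 176/182 = 3.3% |
| 26 | 175 | 189 | 183 | 1 − 183/189 = 3.2% |
| 27 | 182 | 196 | 190 | 1 − 190/196 = 3.1% |

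**Size under Reading A, control arm.** Take completers only, 26 weekly injections, and daily-drug completers at 184 days (last injection on Day 183). With weekly share w, which the documents do not give, the inflation of person-time is 6w / (183w + 184(1 − w)):
- w = 20%: 1.2 / 183.8 = 0.65%
- w = 50%: 3 / 183.5 = 1.6%
- w = 100%: 6 / 183 = 3.3%

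**What uses this denominator.** Only the two incidence rates do. The percentages of patients with events and the Kaplan-Meier curve do not. SAP 2.4.5 makes the safety analyses descriptive, without tests.

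**The case for a change.** The best case for a change is that a SAP should lead to one denominator per rate, and this wording allows two. Reading A is not perverse. It uses the only weekly duration formula in the document, SAP 2.5.3 treats the two duration terms as one, and the daily check works with the 2.4.3.1 base, which could reassure a programmer who then applies the weekly formula. The resulting error would always lower the control rate, and one defining sentence would exclude it.

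Part of this stands: the term is undefined, and the 6-day figure is correct on Reading A. But Reading A needs a formula from a section the note does not cite, and it makes the sentence contradict both its stated definition and the section it does cite. The two tails equal the two hypoglycaemia tails in 2.1.4, which shows what the note is paraphrasing. Checking the derived exposure against the window would expose the 6 days at once.

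The rescue point does not stand. The sentence planning that summary limits it to the on-treatment period before rescue begins. Since exposure is the duration of the period analysed, it stops there too.

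A related point concerns FRC patients eligible for the extension: +1 could pass the window by one day if the last randomized-period injection is recorded on the V28 date. Section 2.1.4 ends that window at V28 explicitly, and it governs. If the slip were made in all of an assumed 230 of 250 FRC patients, it would add 250 × 184 / (230 × 183 + 20 × 184) − 1 = 0.50% to FRC person-time and partly offset the control-arm effect.

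**Conclusion.** No change to the plan follows. The governing definition is already there: hypoglycaemia exposure is the length of the 2.1.4 on-treatment window for the period analysed. The +1/+7 wording is a loose paraphrase with one undefined term, a gap that an analyst fills from the section cited in the same sentence. The discrepancy is zero on the reading that fits that sentence. On the other reading it is 6 days per weekly-drug control patient, about 3% of a completer's exposure and 0.65% to 3.3% of control-arm person-time. Those percentages assume completers, 26 injections for the arm-level range, and weekly shares of 20% to 100%. The rates are descriptive, so neither the primary analysis nor any test or decision rule depends on them. Writing the definition into the programming specification is ordinary good practice and does not require amending the SAP.

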9.2.2.6 Immunogenicity

Antibody variables in FRC group:

- Anti-insulin glargine antibody:
 - Status (Positive, Negative) and titer;
 - Cross-reactivity of anti-insulin glargine antibodies with human insulin.
- Anti-lixisenatide antibody:
 - Status (Positive, Negative) and concentration;
 - Cross-reactivity of anti-lixisenatide antibodies with GLP-1 and glucagon as well as neutralizing effects of these antibodies against lixisenatide, GLP-1 and glucagon.

Sampling time: Blood samples for antibodies will be taken before injection of IMP in the FRC patients: for anti-lixisenatide antibody, at baseline (V3, day 1), V11 (Week 4), V21 (Week 12) and V28 (Week 26), V35 (Week 52, for patient in extension period); for anti-insulin antibody, at baseline (V3, Day 1) and V28 (Week 26), V35 (Week 52, for patient in extension period). Samples will also be taken in case of premature discontinuation from IMP, if possible. One additional sample for potential additional assessments of immunogenicity will be taken when the patients completes the study (either at Week 26, Week 52 or in case of premature discontinuation).

Antibodies handling procedures: Detailed procedures of sample preparation, storage and shipment will be described in the specific laboratory manual.

Bioanalytical method: Antibodies will be determined at centralized laboratories using validated assay methodologies.

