antibody status (Positive, Negative) during 26-week randomized treatment period and during whole study treatment period including 26-week extension period, respectively. A patient is defined as anti-lixisenatide (or anti-insulin glargine) antibody positive during the 26-week randomized treatment period (or whole study treatment period) if the patient is anti-lixisenatide (or anti-insulin glargine) antibody positive at any time during the 26-week randomized treatment period (or whole study treatment period).

The number (%) of patients with at least 1 documented symptomatic hypoglycemia during the 26-week on-treatment period will be assessed by treatment group over time, using weekly time intervals up to 26 weeks, ie, [0-1] week, (1-2] weeks, (2-3] weeks, (3-4] weeks, etc. Similar summaries will be provided for FRC group during the on-treatment period of the whole study, using weekly time intervals up to 52 weeks. In each time interval, the numerator in the calculation of percentages will be the number of patients with at least 1 event occurring in this time interval. Two types of analyses will be included: (1) only the first event will be counted for each patient and all recurrent events will not be included, and the denominator for the calculation of percentages will be the number of patients at risk at the beginning of the time interval who did not experience a first event in the preceding intervals; and (2) the recurrent events in subsequent intervals will be counted once for each patient in the numerator of the corresponding interval, and the denominator for the calculation of percentages will be the number of patients at risk at the beginning of the time interval.

A KM curve will also be provided by treatment group for the time to first documented symptomatic hypoglycemia during the on-treatment period.

The number (%) of patients with at least 1 documented symptomatic hypoglycemia during the on-treatment period, as well as the corresponding number of events, will be summarized as necessary by hour of the day for each treatment group, using the following hour intervals: $\geq 23:00$ to $<06:00$, $\geq 06:00$ to $<10:00$, $\geq 10:00$ to $<14:00$, $\geq 14:00$ to $<18:00$, $\geq 18:00$ to $<23:00$.

Similar analysis may be provided for severe symptomatic hypoglycemia as appropriate.

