2.4.5.2 Analyses of adverse events

Generalities

The primary focus of AE reporting will be on treatment-emergent adverse events (TEAEs). Pre- and post-treatment AEs will be described separately. The adverse events will be summarized by treatment group for the 26-week randomized treatment period and for FRC group for the whole

study treatment period including the 26-week single-arm extension period, respectively, unless specified otherwise.

If an AE date/time of onset (occurrence, worsening, or becoming serious) is incomplete, an imputation algorithm will be used to classify the AE as pre-treatment, treatment-emergent, or post-treatment. The algorithm for imputing date/time of onset will be conservative and will classify an AE as treatment-emergent unless there is definitive information to determine it is pre- or post-treatment. Details on classification of AEs with missing or partial onset dates are provided in [Section 2.5.3](#).

Adverse event incidence tables will present the number (n) and percentage (%) of patients experiencing an AE by primary SOC, HLGT, HLT and PT, sorted by the internationally agreed order for SOCs and alphabetic order for HLGT, HLT and PT within a SOC, for each treatment group. Multiple occurrences of the same event in the same patient will be counted only once in the tables within a treatment phase. The denominator for computation of percentages is the safety population within each treatment.

Sorting within tables should ensure the same presentation for the set of all AEs within the observation period (pre-treatment, treatment-emergent, and post-treatment). For that purpose, the table of all TEAEs presented by primary SOC and PT sorted by the internationally agreed order for SOCs and decreasing frequency for PTs within a SOC will define the presentation order for all other similar tables unless otherwise specified. Sorting of PTs will be based on the results for the FRC group.

The internationally agreed order of SOCs shown below was described in the Introductory Guide MedDRA Version 19.1, September 2016 International Conference on Harmonisation for SOC:

1. Infections and infestations
2. Neoplasms benign and malignant (including cysts and polyps)
3. Blood and lymphatic system disorders
4. Immune system disorders
5. Endocrine disorders
6. Metabolism and nutrition disorders
7. Psychiatric disorders
8. Nervous system disorders
9. Eye disorders
10. Ear and labyrinth disorders
11. Cardiac disorders
12. Vascular disorders

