- All TEAEs by primary and secondary SOC, HLGT, HLT, and PT, showing number (%) of patients with at least 1 TEAE, sorted by internationally agreed order of SOCs. The other levels (HLGT, HLT, PT) will be presented in alphabetic order;
- Kaplan-Meier curves will be provided, when appropriate, for the time to first onset of the following PTs: nausea and vomiting;
- The frequency of TEAEs over time will be provided for nausea and vomiting, using weekly time intervals up to 26 weeks, ie, [0-1] week, (1-2] weeks, (2-3] weeks, (3-4] weeks, etc. Similar summary will be also provided for the FRC group for the whole study treatment period including the extension period, using weekly intervals up to 52 weeks. In each time interval, the numerator in the calculation of percentages will be the number of patients with at least 1 TEAE occurring in this time interval. Two types of analyses will be included: (1) only the first event will be counted for each patient and all recurrent events will not be included, and the denominator for the calculation of percentages will be the number of patients at risk at the beginning of the time interval who did not experience a first event in the preceding intervals; and (2) the recurrent events in subsequent intervals will be counted once for each patient in the numerator of the corresponding interval, and the denominator for the calculation of percentages will be the number of patients at risk at the beginning of the time interval;
- Summaries of common TEAEs (PTs with an incidence $\geq 2\%$ in any treatment group) will be provided as appropriate by demographic factors including gender (Male, Female), age group (<50, ≥ 50 to <65, ≥ 65 to < 75, ≥ 75 years of age), and race (American Indian or Alaska Native, Asian/Oriental, Black, Native Hawaiian or Other Pacific Islander, White, Other), GLP-1 receptor agonist subtype (QD/BID formulations, QW formulations) at screening.
- Summaries of all TEAEs will be provided for FRC group respectively by anti-lixisenatide and anti-insulin glargine antibody status (Positive, Negative) during the 26-week randomized treatment period and during the whole study treatment period including 26-week extension period.

Analysis of all treatment emergent serious adverse event(s)

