- All treatment-emergent SAEs by primary SOC, HLGT, HLT, and PT, showing the number (%) of patients with at least 1 treatment-emergent SAE, sorted by the internationally agreed SOC order. The other levels (HLGT, HLT, PT) will be presented in alphabetical order.

- All treatment-emergent SAEs regardless of relationship and related to IMP, by primary SOC, HLGT, HLT, and PT, showing the number (%) of patients with at least 1 treatment-emergent SAEs, sorted by the internationally agreed SOC order. The other levels (HLGT, HLT, PT) will be presented in alphabetical order.

Analysis of all treatment-emergent adverse event(s) leading to treatment discontinuation

- All TEAEs leading to treatment discontinuation, by primary SOC, HLGT, HLT, and PT, showing the number (%) of patients with at least 1 TEAE leading to treatment discontinuation, sorted by the internationally agreed SOC order. The other levels (HLGT, HLT, PT) will be presented in alphabetical order.

Local tolerability at injection site

The number (%) of patients with local intolerability at injection site will be summarized by PT (PTs coded from the investigator reported terms or PTs coded from ARAC diagnosis terms), sorted by decreasing incidence of PT. Similar summaries will be provided for FRC group respectively by anti-lixisenatide and anti-insulin glargine antibody status (Positive, Negative). All events will be listed.

Allergic reactions

Kaplan-Meier curves will be provided for the time to first onset of events adjudicated as allergic reactions by ARAC. The number (%) of patients with events adjudicated as allergic reactions by ARAC will be summarized by PT (sorted by decreasing incidence of PT) and ARAC diagnosis along with 2 subcategories, events adjudicated as possibly related to IMP and events adjudicated as not related to IMP. Tabulation summaries will be provided as necessary by gender (Male, Female), age group (<50, ≥50 to <65, ≥65 to <75, ≥75 years of age), race (American Indian or Alaska Native, Asian/Oriental, Black, Native Hawaiian or Other Pacific Islander, White, Other). Similar summaries will be provided for FRC group respectively by anti-lixisenatide and anti-insulin glargine antibody status (Positive, Negative).

All the allergic events reported by the investigator on the AE form for suspected allergic event and its associated complementary forms (confirmed or not confirmed by ARAC) will be listed.

Pancreatic-related events

- Increased pancreatic enzymes >2 times ULN

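### Classing FRC patients as antibody-positive if positive at any time in the period builds immortal-time bias into the antibody-by-safety tables, in a direction that depends on the event and the measure

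*SAP*

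**What the plan says.** **Status rule.** SAP 2.4.5.1 defines a patient as positive when "antibody positive at any time during the 26-week randomized treatment period (or whole study treatment period" is met. Negative is not defined.

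**Hypoglycemia measures.** The same section plans the frequency of documented symptomatic hypoglycemia by antibody status and two rates. One is "calculated as the number of patients with at least 1 event / total exposure in patient years"; the other is "calculated as the number of events / total exposure in patient years". Exposure is not split at the first positive sample.

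**Adverse events.** SAP 2.4.5.2 says: "Summaries of all TEAEs will be provided for FRC group respectively by anti-lixisenatide and anti-insulin glargine antibody status (Positive, Negative". It names the same two periods but does not repeat the definition. For injection-site and adjudicated allergic reactions it says only: "Similar summaries will be provided for FRC group respectively by anti-lixisenatide and anti-insulin glargine antibody status (Positive, Negative". These tables are counts and percentages: "Adverse event incidence tables will present the number (n) and percentage (%) of patients experiencing an AE".

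**Sampling.** Protocol 9.2.2.6 schedules blood samples "for anti-lixisenatide antibody, at baseline (V3, day 1), V11 (Week 4), V21 (Week 12) and V28 (Week 26". Anti-insulin antibodies have one scheduled post-baseline sample in the randomized period, at Week 26. Week 52 samples come only from patients in the extension, and Protocol 7.2.5 bars anyone who stopped FRC before Week 26. For leavers: "Samples will also be taken in case of premature discontinuation from IMP, if possible".

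Neither document gives a landmark, a time-updated status or a minimum number of samples for these tables.

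**The concern.** Status is fixed with hindsight. Time and events before the first positive sample are credited to the positive group, and a patient who stays longer has more opportunity to convert and to be found positive. The two groups therefore differ in length of follow-up by construction.

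A reader would use these tables to judge whether antibodies are linked to allergic reactions, injection-site reactions, other TEAEs or hypoglycemia. If the event itself ends treatment, the patient has little time left to become positive, and a harmless or even harmful antibody can look protective. If the event does not end treatment, the longer follow-up of positives raises their percentage, and a harmless antibody can look harmful.

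**Working it through.** The documents give no figure for these tables, so there is none to reproduce. The check asks what the planned measures return when antibodies have no effect. A sound comparison then gives a positive/negative ratio of 1.00.

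**Inputs from the documents.** The status rule, measures and sampling visits above, and 20% drop-out by Week 26 (SAP 1.3).

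**Assumed inputs.** 50% seroconversion by Week 26 (range 20% to 70%); hypoglycemia at 1 per patient-year; an AE at 0.1 per patient-year; every leaver sampled (range 0% to 100%); constant hazards; lasting seroconversion.

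**Formula.** With every leaver sampled, a patient is ever positive exactly when conversion comes before the end of follow-up. Let s be the weekly conversion hazard and h the weekly hazard of leaving:

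P(leaves, negative) = h/(h+s) × [1 − exp(−26(h+s))], with s = ln 2/26 = 0.02666.

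**Step 1: who leaves early.** h = −ln(0.8)/26 = 0.00858.
- P(leaves, negative) = 0.2435 × (1 − 0.8×0.5) = 0.146.
- Negative completers: 0.8×0.5 = 0.400. All negatives: 0.546. All positives: 0.454.
- Leavers among negatives: 0.146/0.546 = 27%. Among positives: (0.200 − 0.146)/0.454 = 12%.

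**Step 2: an AE that always stops treatment.** Other drop-out is set at 15%, so that total leaving stays near 20%. h = −ln(0.85)/26 + 0.1/52.18 = 0.00625 + 0.00192 = 0.00817.
- P(leaves) = 1 − exp(−26×0.00817) = 0.191.
- P(leaves, negative) = 0.2345 × 0.5957 = 0.140.
- Negatives: 0.140 + 0.5×0.809 = 0.544. Positives: 0.456.
- Leavers: 25.7% of negatives, 11.3% of positives. The AE causes the same share of leaving in both groups (0.00192/0.00817 = 0.235), giving 6.0% and 2.7%. Ratio: 0.44.

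**Step 3: hypoglycemia that does not stop treatment, 20% drop-out.** Mean follow-up is 24.9 weeks in positives and 22.0 in negatives. Averaging 1 − exp(−t/52.18) over each group's follow-up t gives 37.7% and 33.6%. Ratio: 1.12.

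**Step 4: ranges, by simulation with the protocol's visits (26 weeks).**

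| Event and measure | Ratio at 50% seroconversion, all leavers sampled | Range over assumed inputs |
|---|---|---|
| AE always stops treatment, % | 0.44 | 0.23 to 0.51 (anti-lixisenatide) |
| AE stops treatment in 25% of cases, % | 0.90 to 0.93 | 0.83 to 0.94 (anti-lixisenatide) |
| Hypoglycemia, never stops treatment, % | 1.12 | 1.00 to 1.26 |
| same, patients with event per patient-year | 0.99 | 0.96 to 1.00 |
| same, events per patient-year | 1.00 | 0.99 to 1.01 |
| Hypoglycemia, 5% of first events stop treatment, % | 1.07 | 1.00 to 1.15 |
| same, patients with event per patient-year | 0.94 | 0.86 to 1.00 |
| same, events per patient-year | 0.96 | 0.93 to 1.01 |

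Over 52 weeks, with 95% of completers assumed to enter the extension, the hypoglycemia percentage ratio is 1.36. With no drop-out, the planned measures return 1.00. For anti-insulin antibodies, the always-stopping AE gives a ratio of 0 if no leaver is sampled and unsampled leavers are called negative. If they are excluded instead, both columns lose the event altogether.

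**Step 5: the remedies under the same null.** A Week 12 landmark gives 0.98 to 1.01 in every scenario. Time-updated status without stratification gives 0.98 to 1.00 when the hazard is constant, but 0.77 or 1.20 when hypoglycemia is twice or half as frequent in the first 8 weeks. Negative time is mostly early time, so the early hazard is read as an antibody effect. Twice-weekly titration in those 8 weeks (Protocol 8.1.4.1) makes a changing hazard plausible. Splitting at Week 8 removes the distortion in this scenario, because the hazard is then constant within each stratum.

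**The case against.** A reader might infer that early leavers are automatically negative, and that all these tables therefore lean towards false protection. The documents do not support that.

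- A sample at premature discontinuation is planned where possible, the end-of-treatment assessments are brought forward for leavers, and leavers stay in scheduled follow-up. SAP 2.1.4.8 counts antibody results up to 28 days after the last injection.
- No rule makes an unsampled patient negative. By default, SAP 2.5.3 leaves patients with missing categorical data out of percentages.
- For hypoglycemia the percentage table leans the other way, and the planned rate of events per patient-year is close to unbiased unless hypoglycemia stops treatment.
- The definition is written only for hypoglycemia. Its use for TEAEs is implied, and for injection-site and allergic reactions it is simply not stated.
- The tables are descriptive, with no test (SAP 2.4.5). The listings of AEs, allergic events and antibody status by visit would let a careful reader check timing.

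All of this stands and limits the point. It does not remove it: the 0.44 already assumes that every leaver is sampled, because a sample at an early stop cannot show antibodies that would have formed later. The missing-data default holds only where nothing else is specified, and SAP 2.4.5.2 sets the AE denominator as the safety population within each treatment. How an unsampled leaver is classed is therefore open.

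**Conclusion.** The point holds in this form: ever-positive status carries immortal-time bias, and its direction depends on the event and the measure. At an assumed 50% seroconversion with all leavers sampled, events that always stop treatment show a strong false protective association (about 0.4 to 0.5). Events that stop treatment in a quarter of cases show a mild one (about 0.9). Hypoglycemia that does not stop treatment shows mild false harm in the percentage table, and its events per patient-year show little bias.

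The sizes rest on assumed seroconversion, event rates and stopping shares that the documents do not give; the mechanism does not. The consequence is limited to descriptive safety tables within the FRC arm. The change is worth making before the tables are programmed, but the primary analysis and sample size are untouched.

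**What to change.** Keep the planned tables and amend the SAP as follows.

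1. For anti-lixisenatide antibodies, add one of two summaries for documented hypoglycemia, TEAEs, injection-site reactions and adjudicated allergic reactions. Either use a Week 12 landmark (status from samples up to Week 12, events and patient-years after it), or use a time-updated rate stratified by time on treatment, for example Weeks 0 to 8 and after Week 8. An unstratified time-updated rate should not be used.
2. State the antibody-status rule for the TEAE, injection-site and allergic-reaction tables in SAP 2.4.5.2.
3. Show patients without a post-baseline antibody sample as their own category, not as negative.
4. Label the anti-insulin tables as association only. A landmark does not suit them, because no sample is scheduled between baseline and Week 26. Do not restrict them to patients with a Week 26 sample, since that could drop the event-driven leavers.

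The cost is SAP wording and some extra programming; the samples and event dates are already planned. The landmark summary leaves out events before Week 12, so it supplements the full-period tables and does not replace them.
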